## **9. REGULATORY CONSIDERATIONS**

### **9.1 Institutional Review of Protocol**

The protocol, the proposed informed consent and all forms of participant information related to the study (e.g. advertisements used to recruit participants) will be reviewed and approved by the Stanford IRB. Any changes made to the protocol will be submitted as a modification and will be approved by the IRB prior to implementation. The Protocol Director will disseminate the protocol amendment information to all participating investigators.

### **9.2 Data Management Plan**

Electronic CRF's and patient records will both be stored electronically using OnCore.

### **9.3 Data and Safety Monitoring**

During the clinical investigation, the Protocol Director will evaluate the progress of the trial, including periodic assessments of data quality and timeliness, participant recruitment, accrual and retention, participant risk versus benefit, performance of trial sites, and other factors that can affect study outcome. Monitoring of the trial will occur every 12 weeks and a record of monitoring activities will be maintained by the study team.

The Stanford Cancer Institute Data and Safety Monitoring Committee (DSMC) will audit study related activities to determine whether the study has been conducted in accordance with the protocol, local standard operating procedures, FDA regulations, and Good Clinical Practice (GCP). This may include review of regulatory binders, case report forms, eligibility checklists, and source documents. In addition, the DSMC will regularly review serious adverse events and protocol deviations associated with the research to ensure the protection of human subjects. Results of DSMC audits will be communicated to the IRB and the appropriate regulatory authorities at the time of continuing review, or in an expedited fashion, as needed.

## **10. MEASUREMENTS**

### **10.1 Primary outcome measure**

We will evaluate the image quality of the lesions detected with the digital PET/CT scanner

and compare with the image quality of the lesions seen on the standard of care pre-therapy  $^{99m}\text{Tc}$ -MAA SPECT/CT.

## **10.2 Measurement Methods**

We will use a 5-point Likert scale to assess image quality.

## **10.3 Measurement Time Points**

Images will be analyzed after completion of scanning and processing. Goal is to complete this within one month of acquisition.

## **10.4 Response Review**

The 5-point Likert scale will be determined by Nuclear Medicine physicians blinded to the diagnosis and results of the other scan, in a randomized order to avoid bias. Two physicians will review all scans independently. Both scans of a given patient will be analyzed by one physician, then separately by the second physician.

## **10.5 Secondary outcome measure**

We will assess the radiopharmaceutical distribution and dosimetry accuracy of  $^{90}\text{Y}$  PET/CT by comparing visual distribution discrepancies (if any) and numerical values calculated by SurePlan from both  $^{99m}\text{Tc}$  MAA SPECT/CT and  $^{90}\text{Y}$  PET/CT images.

## **10.6 Measurement Methods**

We will use SurePlan software to edge-contour and calculate tumor radiation absorbed dose values in both  $^{99m}\text{Tc}$  MAA SPECT/CT and  $^{90}\text{Y}$  PET/CT images. This software will convert counts/pixel on the images to radiation absorbed dose measure in Gray.

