### 1.2 Secondary Objective

- To determine the superior accuracy in both distribution and dosimetry of  $^{90}\text{Y}$  PET/CT post SIRT imaging compared to  $^{99\text{m}}\text{Tc}$  MAA planar and SPECT/CT imaging

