## **5.2 Details of Imaging (i.e. dynamic, static, number of scans, etc.)**

Patients will have  $^{99m}\text{Tc}$  MAA planar and SPECT/CT imaging as part of the standard SIRT planning protocol. These images are acquired after administration of 4 mCi of  $^{99m}\text{Tc}$  MAA in the Interventional Radiology suite. The patient will then be given  $^{90}\text{Y}$  Spheres (Glass or Resin), and after SIRT procedure, will be arrive to NM for digital PET/CT image acquisition with diagnostic contrast enhanced CT of the abdomen. We will be administering 50mL of iodinated contrast through IV during the CT scan. Next, PET images will be acquired in 3D mode using a single bed located over the liver, with a total acquisition time of approximately 30-minutes. The PET emission scan is corrected using the segmented attenuation data from the CT scan. The PET images are reconstructed both with a standard iterative algorithm (OSEM, two iterative steps, 28 subsets), as well as a regularized reconstruction algorithm provided by GE Healthcare. All images are reformatted into axial, coronal, and sagittal views and viewed with the software available in the Nuclear Medicine and Molecular Imaging Clinic (MIM Software, Cleveland, OH).

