## **5.3 Details of processing/analysis**

The  $^{99m}\text{Tc}$  MAA planar and SPECT/CT imaging and the PET/CT scans will be interpreted by ABNM certified Nuclear Medicine physicians. All investigators have significant clinical experience and will be blinded to the participant's medical history and the results of other imaging modalities. A consensus read will be obtained for each scan to assess image quality. Each lesion will be tabulated and a comparison of lesion detection and radiation absorbed dose by each scanner will be conducted.

Currently,  $^{99m}\text{Tc}$  MAA planar and SPECT/CT images only simulate  $^{90}\text{Y}$  radiopharmaceutical biodistribution within the liver and tumor(s). Incorporating SurePlan software (MIM) to analyze the PET/CT images will determine final dose-volume histogram (DVH) within the liver and tumor (s) post  $^{90}\text{Y}$  injection. Additionally,  $^{90}\text{Y}$  PET/CT and  $^{99m}\text{Tc}$  MAA planar and SPECT/CT biodistribution images can be compared to evaluate  $^{99m}\text{Tc}$  MAA simulation accuracy. Results of this image comparison could potentially impact clinical decision-making moving forward. This information will be reported and shared with the referring physicians involved in the care of the patient.

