## **10.8 Response Review**

After radiation absorbed dose is measured in both  $^{99m}\text{Tc}$  MAA SPECT/CT and  $^{90}\text{Y}$  PET/CT images, the values will be compared on a lesion-by-lesion basis.

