### **11.5 Statistical Analysis**

Statistical analysis is not required for this study since the comparison is between two separate modalities with inherently different properties.

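### Lesion doses from SPECT and PET are compared with no stated handling of unequal spatial resolution, so in small tumours a blur difference could be misread as MAA simulation error

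*Combined protocol and SAP*

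**What the plan says.** Section 10.6 states: "We will use SurePlan software to edge-contour and calculate tumor radiation absorbed dose values in both" the MAA SPECT/CT and the 90Y PET/CT, and adds: "This software will convert counts/pixel on the images to radiation absorbed dose measure in Gray". Under section 10.8, "the values will be compared on a lesion-by-lesion basis".

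Two questions draw on this pair of images. Sections 1.2 and 10.5 ask about the accuracy of 90Y PET imaging. The objective reads "To determine the superior accuracy in both distribution and dosimetry of" PET relative to MAA imaging, and the outcome uses "numerical values calculated by SurePlan from both" modalities. Section 5.3 asks something else, namely how accurate the MAA simulation was: the two sets of "biodistribution images can be compared to evaluate" it. The same section says that the results could influence clinical decisions and will be shared with referring physicians.

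Section 5.2 reconstructs the PET data with a standard OSEM algorithm "as well as a regularized reconstruction algorithm provided by GE Healthcare" and does not say which one supplies the dose. Section 11.5 plans no statistical analysis because "the comparison is between two separate modalities with inherently different properties". No section gives the spatial resolution of either modality, a resolution-matching or recovery step, a minimum lesion size, or reporting by lesion size.

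**The concern.** Limited resolution spreads the signal of a tumour into its surroundings and that of the surroundings into the tumour. The measured tumour mean is therefore pulled towards the liver value, more so when the blur is wide or the tumour small. If the two images are blurred to different degrees, the same true distribution gives two different doses in Gray. The discrepancy depends on lesion size and is a bias, so enrolling all 75 patients would not reduce it.

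The question in section 5.3 is the one at risk. A gap between the PET and MAA doses of a small lesion could be reported as a failure of MAA to predict 90Y deposition when it reflects only how the two cameras render the same object. The plan notes that the modalities differ, but uses this as a reason to omit analysis and not as something to control for.

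**Working it through.** The documents state no resolution, lesion size, uptake ratio or recovery figure, so there is no planned number to reproduce. The check asks what the planned comparison returns when MAA is a perfect predictor (true ratio 1.00).

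**Inputs from the documents.** Dose comes from image counts in both modalities (10.6), the comparison is by lesion (10.8), and no lesion size or uptake requirement is set (3.1).

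**Assumed inputs.** A uniform spherical tumour of diameter D in uniform liver; 3D Gaussian blur; the true contour on both images; PET/SPECT FWHM pairs 5/10, 6/12, 6/15 and 8/15 mm; tumour-to-liver ratio T of 2, 4 and 8.

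**Formulas.** With R = D/2 and σ = FWHM/2.355, the blurred unit sphere at radius r is

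g(r) = ½[erf((R−r)/(σ√2)) + erf((R+r)/(σ√2))] − σ/(r√(2π)) × [exp(−(R−r)²/2σ²) − exp(−(R+r)²/2σ²)].

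Recovery is RC = (3/R³)∫₀ᴿ g(r) r² dr. With liver set to 1, the measured tumour mean is 1 + (T−1)RC, so

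PET/MAA = [1 + (T−1)RC_PET] / [1 + (T−1)RC_SPECT].

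**Recovery coefficients.**

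| FWHM (mm) | D = 20 mm | D = 30 mm | D = 60 mm |
|---|---|---|---|
| 5 | 0.750 | 0.832 | 0.915 |
| 6 | 0.702 | 0.799 | 0.899 |
| 8 | 0.609 | 0.734 | 0.865 |
| 10 | 0.522 | 0.670 | 0.832 |
| 12 | 0.443 | 0.609 | 0.799 |
| 15 | 0.340 | 0.522 | 0.750 |

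**Central case, 6/12 mm, T = 4.**
- 20 mm: (1 + 3×0.702)/(1 + 3×0.443) = 3.106/2.329 = 1.33
- 30 mm: 3.397/2.827 = 1.20
- 60 mm: 3.697/3.397 = 1.09

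**Range over the four pairs and T = 2 to 8.** The lowest ratio is at 5/10 mm with T = 2, the highest at 6/15 mm with T = 8.
- 20 mm: 1.750/1.522 = 1.15 to 5.914/3.380 = 1.75
- 30 mm: 1.832/1.670 = 1.10 to 6.593/4.654 = 1.42
- 60 mm: 1.915/1.832 = 1.05 to 7.293/6.250 = 1.17

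Adding the pairs 8/10 and 5/15 mm widens the 20 mm range to about 1.06-1.85.

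**When the effect vanishes or reverses (20 mm).**
- T = 1: the ratio is 1.00 for any pair. Equal resolution also gives 1.00.
- T = 0.5: (1 − 0.5×0.702)/(1 − 0.5×0.340) = 0.649/0.830 = 0.78 for 6/15 mm, and 0.625/0.739 = 0.85 for 5/10 mm. The other two pairs lie between.
- PET coarser than SPECT (12 versus 10 mm, T = 5): 0.90.

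**Blur common to both scans, such as breathing (6/12 mm, T = 4, 20 mm).** Widths add in quadrature. Adding 10 mm gives √(6²+10²) = 11.7 and √(12²+10²) = 15.6 mm, and the ratio falls from 1.33 to about 1.2 (1.20 or 1.21 depending on the numerical method). Adding 15 mm gives 16.2 and 19.2 mm, and the ratio falls to 1.13.

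**Separate edges.** Section 10.6 plans edge contours in both images, so the model was also run with a maximum-gradient edge found separately on each. At 6/15 mm and T = 5 the 20 mm ratio is 1.60, against 1.61 with the shared true contour. At 60 mm it is 1.11 against 1.15. Separate edges do not remove the effect.

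**After matching.** For 6/12 mm the added kernel is √(12²−6²) = 10.4 mm. Both images then have the same RC, and with the same contour on both the ratio is exactly 1.00 at every diameter.

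**The case against.** Every resolution figure above is assumed. Section 2.1 credits digital PET with sensitivity and temporal resolution, not finer spatial resolution, and section 11.5 does not say which properties differ. A reader might infer that PET will always read higher than MAA. The documents do not support that: it needs PET to be the finer image and the tumour to take up more than liver, and the plan establishes neither. Nor is the plan's silence proof that SurePlan or the SPECT reconstruction applies no resolution recovery.

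The model is also idealised. It has no noise, scatter, motion or uneven uptake, and its main figures use a true contour instead of the planned edge contours. Section 5.2 mentions no respiratory gating for an acquisition of about 30 minutes, so shared motion blur is plausible and would reduce the effect.

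Finally, resolution is a nuisance only for the question in section 5.3. For sections 1.2 and 10.5, poor recovery on SPECT is a genuine error of MAA-image dosimetry and belongs in the comparison. A reader might also infer that a higher PET dose would count as superiority, but section 1.2 does not say so. And since section 10.8 defines no estimator, choosing one comes before this refinement.

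These points stand. They limit the sign, the size and the scope of the concern. They leave the gap itself: the plan gives no means of separating MAA prediction error from a difference in blur.

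**Conclusion.** The concern holds conditionally. As written, the comparison can show a lesion-size-dependent difference under perfect MAA prediction. If PET is effectively finer, PET is expected to read higher in small tumours with uptake above liver, and lower where uptake is below liver. The modelled excess, roughly 15% to 75% at 20 mm and 5% to 17% at 60 mm, illustrates the possible size and is not a forecast for these scanners. Common blur of 10-15 mm would bring the central 20 mm case down from 33% to about 20% or 13%.

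The consequence is limited to a secondary outcome, and within it to statements on MAA simulation accuracy. It does not follow that the native comparison is invalid, or that small lesions should be set aside: once resolution is matched, the model gives no resolution-based reason to drop them.

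**What to change.** In section 10.6, name the PET reconstruction used for dose. Compute each PET lesion dose twice: on the native image, and after smoothing that same reconstruction to the effective resolution of the reconstructed SPECT. Use the same lesion contour for both PET values. If SurePlan or the SPECT reconstruction already applies resolution recovery, say so and match to the resulting resolution.

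In section 10.8, base any statement on MAA simulation accuracy (5.3) on the matched value. Keep the native PET-versus-MAA comparison beside it for the imaging-accuracy objective (1.2, 10.5). Show both by lesion diameter and exclude no small lesions.

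The cost is one extra filter and dose calculation per PET scan, on images already acquired; no new scan, reader or patient is needed. The matched value depends on an estimated resolution, so state how that was obtained. Matching does not remove differences between the PET and SPECT contours, which remain a separate source of disagreement.

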## **10.7 Measurement Time Points**

Images will be analyzed after completion of scanning and processing. Goal is to complete this within one month of acquisition.

## **10.8 Response Review**

After radiation absorbed dose is measured in both  $^{99m}\text{Tc}$  MAA SPECT/CT and  $^{90}\text{Y}$  PET/CT images, the values will be compared on a lesion-by-lesion basis.

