# **3. PARTICIPANT SELECTION AND ENROLLMENT PROCEDURES**

## **3.1 Inclusion Criteria**

- Patient is  $\geq$  18 years old at the time of the scan
- Patient provides written informed consent
- Patient is referred for  $^{90}\text{Y}$  SIRT radioembolization of liver tumor(s)
- Patient is capable of complying with study procedures

- Patient is able to remain still for duration of imaging procedure (approximately 30 minutes total for digital PET/CT)

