### **11.3. Accrual estimates**

We expect accrual of 75 patients. There are approximately 100 patients receiving SIRT each year at Stanford University. We plan to enroll 25 participants/year (33%) and this is easily achievable given our experience with other protocols.

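### The secondary dose comparison has no planned summary for clustered lesions, and the design cannot test the superior accuracy that objective 1.2 sets out to determine

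*Combined protocol and SAP*

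**What the plan says.** Objective 1.2 of the combined protocol and SAP is directional: "To determine the superior accuracy in both distribution and dosimetry of" 90Y PET/CT, set against 99mTc MAA imaging. Section 10.5 pursues it by "comparing visual distribution discrepancies (if any) and numerical values calculated by SurePlan from both" scans. Section 10.6 fixes the variable as tumor absorbed dose in Gray, and section 10.8 adds that "the values will be compared on a lesion-by-lesion basis".

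Section 3.1 admits patients with one or more liver tumors and sets no maximum. Section 5.3 says "Each lesion will be tabulated and a comparison of lesion detection and radiation absorbed dose by each scanner will be conducted", with no index-lesion or selection rule. Section 5.3 also describes the MAA images as only simulating where the 90Y will go, gives the PET/CT analysis the role of fixing the final dose-volume histogram, and proposes comparing the two to judge how accurate the MAA simulation was.

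Section 11.5 reads: "Statistical analysis is not required for this study since the comparison is between two separate modalities with inherently different properties". Section 11.3 gives the only sample figure: "We expect accrual of 75 patients".

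**The concern.** There are two gaps, and the first comes from section 11.5.

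1. **No summary.** The plan names the variable, the unit and the pairing. It does not say what summary of the paired doses answers objective 1.2, whether patients or lesions carry equal weight, how lesions are matched between scans, or how correlation between lesions in one patient is handled. These choices would be made after the data are seen. The reason given in section 11.5 does not remove the need, because sections 10.5, 10.6 and 10.8 put both modalities on one scale, in Gray, and compare them.

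2. **No test of accuracy.** Accuracy needs a standard outside the two methods compared. Section 10.5 names none, and section 5.3 in effect uses one of the two, the PET/CT, as the standard.

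At stake is the dosimetry conclusion under objective 1.2: its precision could be overstated, and its claim of superiority would not be supported.

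**Working it through.** **Sample figure.** 25 patients per year (11.3) × 3 years (36 months, 3.4.1) = 75. This is an accrual estimate. No alpha, power, effect size or SD is given, so there is no statistical derivation to reproduce.

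**Inputs.** Only n = 75 comes from the documents. Lesions per patient (m), within-patient correlation of the paired log dose ratio (ICC), dose ratios and SDs are all assumed below.

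**Precision, only if lesions were pooled as independent.** Design effect DE = 1 + (m − 1) × ICC. The interval is too narrow by 1 − 1/√DE. Approximate coverage of a nominal 95% interval uses 1.96/√DE.

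| m | ICC | DE | Interval too narrow by | Coverage |
|---|---|---|---|---|
| 1 | any | 1.0 | 0 | 95% |
| 2 | 0.1 | 1.1 | 4.7% | 93.8% |
| 3 | 0.5 | 2.0 | 29.3% | 83.4% |
| 5 | 0.7 | 3.8 | 48.7% | 68.5% |

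At ICC 0 there is no effect. At m = 3 and ICC −0.1, DE = 0.8 and the interval is 12% too wide. In a simulation (20,000 runs, 75 patients, m = 3, ICC 0.5), a 5% test on pooled lesions rejected a true null 16.2% of the time; a test on one mean per patient did so 5.0% of the time.

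**Weighting.** Assume 60 patients with 1 lesion and 15 with 5, so 60 + 75 = 135 lesions. The 15 patients are 15/75 = 0.20 of patients but 75/135 = 0.556 of lesions. Let the dose ratio be 1.0 in the other 60.
- Ratio 1.5 in the 15: pooled exp(0.556 × ln 1.5) = 1.25; per patient exp(0.20 × ln 1.5) = 1.08.
- Ratio 1.1 in the 15: pooled 1.05; per patient 1.02.
- Ratio 1.5 in a random 20% of patients, unrelated to lesion count: both average 1.08, so there is no shift.

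**Accuracy.** For a matched lesion, log(PET dose) − log(MAA dose) is the log error of PET minus the log error of MAA: one observed quantity, two unknowns. An observed ratio of 1.5 fits PET reading 1.5 times the true dose with MAA correct. It fits equally well PET correct and MAA reading 1/1.5 = 0.67 of the true dose. If PET is taken as the reference, as section 5.3 implies, its error is zero by definition and every discrepancy counts against MAA. Either way these data cannot show PET to be superior.

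**What a mean ratio leaves out.** Two lesions with ratios 2.0 and 0.5 have mean log ratio (ln 2 + ln 0.5)/2 = 0, a mean ratio of exactly 1.0 despite strong discordance. A mean measures average bias; agreement also needs the spread.

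**Precision of a patient-level mean.** Half-width = t(0.975, 74)/√75 = 1.993/8.660 = 0.230 SD of the patient-mean log ratio. That is a factor exp(0.230 × 0.3) = 1.07 at SD 0.3 and exp(0.230 × 0.7) = 1.17 at SD 0.7. With 50 evaluable patients it is 0.284 SD.

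**The case against.** The strongest reply is that section 11.5 plans no test or interval, so there is nothing for clustering to distort, and every input except n = 75 is assumed. That stands as far as it goes. A reader might infer that the plan has an inflated error rate or a biased estimate. The documents do not support this: the precision loss arises only under a later pooled analysis with positive correlation, and the weighting shift only if lesion counts are unequal and related to the dose ratio. But the reply does not supply the missing summary. A study that sets out to determine superior accuracy must report the paired doses in some form.

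Three other stronger readings also fail.

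- A reader might take lesion-by-lesion comparison as an error in itself. It is not: pairing the same lesion on both scans is sound, and lesion weighting is a legitimate choice if it is stated.
- A reader might say the protocol has no reference at all. Section 5.3 gives PET/CT that working role. The difficulty is that this makes superiority circular.
- Section 5.3 says "Results of this image comparison could potentially impact clinical decision-making moving forward", from which a reader might infer that a poorly weighted pooled mean would misdirect care. The next sentence there concerns sharing information with physicians treating the individual patient, and patient-level reporting does not depend on how a pooled mean is weighted.

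**Conclusion.** The point holds for the secondary dose outcome. Section 11.5 withholds any analysis from an objective that calls for a comparative conclusion, so the plan as written cannot answer its dose question. Whatever summary is chosen, comparing the two scans with each other, or with PET as the working reference, cannot establish that PET is the more accurate.

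The size cannot be taken from the documents. Under pooling as independent lesions, the interval would be about 5% to 49% too narrow over the assumed range (2 lesions, ICC 0.1, to 5 lesions, ICC 0.7), and unaffected at 1 lesion or ICC 0. Several lesions per patient is implied by sections 3.1 and 5.3, not stated outright. The accuracy limit depends on none of these assumptions. Nothing here bears on the primary image-quality outcome.

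**What to change.** For the dose outcome, replace the statement in section 11.5 with a paragraph such as the following, and refer to it in section 10.8:

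> For each lesion with a measurable dose on both scans, the log absorbed-dose ratio (90Y PET/CT over 99mTc MAA SPECT/CT) is calculated. Average bias is the mean of patient means with a 95% t interval over patients, back-transformed to a ratio. Lesion-level 95% limits of agreement are reported using between- and within-patient variance components. A lesion-weighted mean with patient-clustered standard errors is a sensitivity analysis. Lesions seen, or with measurable dose, on only one scan are reported as counts with patient-clustered intervals. The lesion-matching rule is fixed before doses are compared.

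For dosimetry, reword objective 1.2 and section 10.5 to agreement between the modalities, or to how well MAA predicts the post-therapy PET dose, in place of superior accuracy. Make the choice consistent with section 5.3.

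In a simulation of 20,000 runs (75 patients, each with a 20% chance of 5 lesions and otherwise 1, lesion SD 0.5, ICC 0.1 to 0.7), the t interval over patient means covered 94.8% to 95.3%. Where the ratio was unrelated to lesion count, an independent-lesion interval covered 90%, 81% and 78% at ICC 0.1, 0.5 and 0.7.

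The cost is a paragraph, a cross-reference and the rewording, with no new scans. The downsides are possibly wider intervals, a little more analysis and lesion-matching work, a main ratio limited to lesions measured on both scans (lesions missed by one scan appear only in the counts), and a more modest conclusion.
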